## Study Protocol

### Background

The goal of this campaign is to reduce unnecessary emergency department (ED) visits/encourage patients with low acuity visits to follow up with an appropriate provider and/or to seek care outside of the ED in the future. In this campaign, patients will be assigned to receive or not receive outreach following ED discharge that is aligned with the goal. Outreach will occur via a text message, as well as information added to the patient's after visit summary (AVS), and will include one or more calls to action that make patients aware of other Geisinger resources and avenues through which they can seek care outside of the ED. These may include, but are not limited to, walk-in urgent care, virtual urgent care, primary care provider (PCP) appointments, and/or other ways in which to contact Geisinger. The study will assess whether ED use differs across patients in different outreach conditions. It will also examine whether patients followed through on the message-specific calls to action in the messages differently across conditions.

### Objectives

The study will involve randomized assignment of patients to different versions of outreach, including a treatment arm that encourages patients in non-emergent situations to call their primary care provider's office first and, if unavailable, to try urgent care (or other options, as described next). Patients with a Geisinger PCP are also provided with the appropriate contact number for their PCP, given hyperlinks to Geisinger's urgent care website, and encouraged to consider other same-day care options via a hyperlink to Geisinger's corresponding website. Patients without a Geisinger PCP are encouraged to consider Geisinger's virtual (telehealth) care, with a corresponding hyperlink. Both SMS text messages (at 1 day, 22 days, and 50 days post-discharge) and AVS (printed or available via patient portal upon discharge) will be used for active outreach. The control arm will receive the current standard system outreach and AVS. Data will be analyzed to determine which version is most effective at reducing ED use.

### Design

This study is a randomized controlled trial with two study arms. Patients will be randomized to receive or not receive SMS texts and a modified AVS upon ED discharge.

### Methods

At the time of an eligible patient's discharge from the ED, that patient will be assigned to one of the following study arms, based on which of several ranges of randomized numbers that patient was originally assigned in their electronic chart:

1. **Current standard practice (control arm):** Patients in this arm will receive the current standard AVS and whatever typical system outreach occurs.
2. **Same-day care alternatives (treatment arm):** Patients in this arm will receive suggestions for non-ED alternatives for same-day care.
  - a. Those with a Geisinger PCP will also be provided with:
    - i. PCP contact number
    - ii. Hyperlink to Geisinger's urgent care website
    - iii. Hyperlink to Geisinger website detailing same-day care options

- b. Those without a Geisinger PCP will also be provided with a hyperlink to Geisinger's virtual care option.

## **Power Analysis**

With 5,524 patients, we would have 80% power to detect a 3.0% absolute decrease in ED visits between active and control arms, with two-tailed alpha of .15, assuming a 41% baseline rate of subsequent ED visits within 120 days. The target effect size and number of patients are largely informed by practical considerations regarding the acceptable duration of the intervention (approximately 6 months), with an effect deemed useful if achieved.

## **Project Status**

The intervention launched on April 25, 2024, but no data have been analyzed as of the time this document was uploaded.

Patients without GHP insurance who received or would have received their first message between 5/14/24 and 6/6/24 ( $N = 662$ ) will be removed from the analysis due to unexpected message filtering and restrictions imposed by one of the cell service carriers.

Because of the unforeseen analysis exclusions, we will collect data from an additional 662 patients. Our updated target sample size is 6,186.

## **Statistical Analysis Plan**

### **Planned Analyses**

**Primary Outcome:** ED visit [Time Frame: within 120 days following day of discharge]

**Question:** Does outreach decrease ED visits when including information about same-day care?

**Analysis (Confirmatory):** We will test the hypothesis that SMS text plus AVS outreach decreases the likelihood patients will visit the ED in the 120 days following day of discharge. We will run an OLS regression including a categorical predictor variable coding for experimental arm (0 = control arm, 1 = treatment arm).

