### **Other Pre-specified Outcomes**

We will run the analysis described above on the following additional outcomes:

1. PCP appointment scheduled

PCP appointment scheduled (yes/no)

[Time Frame: within 60 days following day of discharge]

2. PCP visit

PCP appointment attended (yes/no)

[Time Frame: within 60 days following day of discharge]

3. Telehealth appointment scheduled

Telehealth appointment scheduled (yes/no)

[Time Frame: within 60 days following day of discharge]

4. Telehealth appointment attended

Telehealth appointment attended (yes/no)

[Time Frame: within 60 days following day of discharge]

5. Urgent care visit

Urgent care appointment attended (yes/no)

[Time Frame: within 60 days following day of discharge]

6. Call made to PCP

Record of patient call to PCP (yes/no)

[Time Frame: within 60 days following day of discharge]

7. Any of the suggested actions taken

PCP called or visited, urgent care visited, telehealth appointment attended, or PCP or telehealth appointment scheduled (yes/no)

[Time Frame: within 60 days following day of discharge]

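### Optional precision gain: the confirmatory OLS has arm as its only named term although Geisinger PCP and GHP status are held; the gain is probably small unless prior ED visits can be added

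*Combined protocol and SAP*

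**What the plan says.** The confirmatory analysis of any ED visit within 120 days is described in the SAP under Planned Analyses: "We will run an OLS regression including a categorical predictor variable coding for experimental arm", with arm coded 0 or 1. Under Other Pre-specified Outcomes the plan adds: "We will run the analysis described above on the following additional outcomes", and seven binary outcomes follow. No covariate or stratification factor is named in either section. The Analysis Notes defend OLS for a binary outcome but say nothing about covariates.

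Two patient characteristics are nevertheless already in use:

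- **Geisinger PCP status** decides what the message contains. Objectives: "Patients with a Geisinger PCP are also provided with the appropriate contact number for their PCP"; the Methods list of treatment-arm content does the same ("Those with a Geisinger PCP will also be provided with"), with different content for the others.
- **GHP insurance status** defines the carrier-related exclusion in both arms. Project Status: "Patients without GHP insurance who received or would have received their first message" in a stated window are removed.

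Project Status also says that "no data have been analyzed as of the time this document was uploaded". Prior ED use is not mentioned anywhere.

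**The concern.** In a randomised trial, adding covariates fixed before the index discharge to an OLS model leaves the estimand, the difference in the probability of an ED visit, unchanged and removes outcome variance that those covariates explain. The plan leaves that precision unused. Precision is scarce here: the Power Analysis section says the sample size was set largely by the acceptable duration of the intervention, and the target power is 80% at a two-sided alpha of .15.

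Timing is the other consideration. Covariates are credible in a confirmatory model only if they are named before outcomes are examined; chosen afterwards, they invite the suspicion that they were picked for the result. The plan reported no analysis at upload. Its status since then is unknown.

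What is at stake is a somewhat smaller standard error. Neither bias nor type I error is in question.

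**Working it through.** **Inputs.** From Power Analysis: N = 5,524, control rate 41%, decrease 3.0 points (so 38% under treatment), two-sided alpha .15, power 80%. From Project Status: 6,186 − 662 = 5,524 analysed. Assumed, because the documents do not say: 1:1 allocation (2,762 per arm), R-squared of the covariates, their prevalences, and their association with ED visits.

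**Step 1: reproduce the plan's figure.** The plan says: "With 5,524 patients, we would have 80% power to detect a 3.0% absolute decrease in ED visits between active and control arms". With mean rate p = .395, z = 1.4395 (alpha .15, two-sided) and 0.8416 (80% power):

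n per arm = [1.4395·√(2 × .395 × .605) + 0.8416·√(.41 × .59 + .38 × .62)]² / .03² = 2,762.5, rounded up to 2,763, or 5,526 in total. The stated 5,524 reproduces, and power at 2,762 per arm is 79.99%.

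**Step 2: effect of adjustment.** The residual variance is .395 × .605 × (1 − R²) = .2390 × (1 − R²), so

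SE = √(2 × .2390 × (1 − R²) / 2,762), and power = Φ(.03/SE − 1.4395).

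At R² = 0, SE = .01316 and power = Φ(2.281 − 1.440) = 80.0%. The detectable difference at 80% power is (1.4395 + 0.8416) × SE. The equivalent N is 5,524/(1 − R²).

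| Assumed R² | Power | Detectable difference (points) | Equivalent N |
|---|---|---|---|
| 0 | 80.0% | 3.00 | 5,524 |
| .01 | 80.3% | 2.99 | 5,580 |
| .02 | 80.6% | 2.97 | 5,637 |
| .05 | 81.6% | 2.92 | 5,815 |
| .10 | 83.3% | 2.85 | 6,138 |
| .15 | 85.0% | 2.77 | 6,499 |

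Gaining 1, 2 or 3 power points needs R² of about .03, .06 or .09.

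**Step 3: what PCP and GHP status could supply.** A binary covariate with share q and a gap g in ED-visit rates between its levels contributes R² = q(1 − q)g²/.2390. With q = .5, R² of about .031 requires g = √(.031 × .2390/.25) = .17, a gap of about 17 points from one variable. For two independent covariates:

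| Split of each | Gap 5 points | Gap 10 points | Gap 15 points |
|---|---|---|---|
| 50/50: R² | .005 | .021 | .047 |
| 50/50: power | 80.2% | 80.7% | 81.5% |
| 80/20: R² | .003 | .013 | .030 |
| 80/20: power | 80.1% | 80.4% | 81.0% |

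For a given gap, the 50/50 split is the most favourable.

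**Step 4: simulation check** (4,000 replicates, N = 5,524, HC2 standard errors, true effect −3.0 points; Monte Carlo error of each power figure about 0.6 points). With two 50/50 covariates and 10-point gaps (R² .023), the mean estimate was −3.02 both unadjusted and adjusted, and power was 79.7% against 80.7%. Adding a prior-ED count with an assumed 15 points per visit (R² .10), the mean estimate was −3.00 for both, and power was 80.8% against 83.8%.

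**The case against.** The strongest reply is that nothing is wrong. An arm-only OLS is legitimate, transparent and pre-specified, and it meets its power target. For the two variables that the documents do show, gaps of 5 to 10 points buy 0.2 to 0.7 power points at best, and less with unequal splits or overlap between PCP and GHP status. No passage links either variable to ED visits, so a gain of zero is equally consistent with the plan. The only material gain comes from prior ED use, which the documents never mention. **All of this stands**, and it is why the point is optional.

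A second reply is that main-effects adjustment need not improve precision if allocation is unequal and the effect differs by PCP status. The allocation ratio is not stated, and message content does differ by PCP status, so this is fair in principle. It did not matter in practice. I simulated 3,000 trials at each of three allocations, with two 50/50 covariates, 10-point gaps and an effect of −6 points in one PCP group and 0 in the other. The empirical standard error, unadjusted against adjusted, was 1.31 vs 1.30 points at 50/50, 1.39 vs 1.38 at 67/33 and 1.63 vs 1.61 at 80/20, with mean estimates near −3.0 throughout.

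A third reply is that robust standard errors are not shown to be needed. At 1:1 that is right: the arm variances are nearly equal (.41 × .59 = .242 and .38 × .62 = .236). They are a safeguard because the ratio is unstated.

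Finally, this would be another post-launch change to the plan, and a covariate included only if obtainable leaves the model open. That is fair, and it is why availability must be settled before outcomes are examined.

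**Conclusion.** The point holds as an optional improvement. Arm is the only term named, two usable covariates are already held, and the planned analysis is valid without them. The wording of the model does not literally exclude covariates, but none is specified.

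PCP and GHP status alone probably add under one power point for the primary outcome. Reaching about 83% to 85% needs R-squared of .10 to .15, which would depend on a stronger predictor such as prior ED visits. That such visits could be extracted in the same way as the outcome is an inference, and how complete they would be is unknown, notably for patients without a Geisinger PCP.

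The power figures rest on 1:1 allocation and assumed R-squared values. Confidence in the size of the gain is therefore moderate at most.

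**What to change.** Before any data are analysed, amend the SAP as follows.

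1. Specify the primary model as OLS of 120-day ED visit on arm, Geisinger PCP status (yes/no) and GHP insurance status (yes/no), both fixed as of the index discharge.
2. If it can be extracted for all patients, add the number of ED visits in a fixed look-back period before the index discharge. Decide this on availability alone, before outcomes are examined. If it cannot be extracted for all, leave it out and do not drop patients.
3. Use HC2 or HC3 standard errors.
4. Report the unadjusted difference as a check.
5. Use the same model for the seven other outcomes.

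If analysis has already begun, keep the arm-only model as confirmatory and label the adjusted one a sensitivity analysis.

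The cost is a few SAP sentences (covariate list, date at which status is fixed, look-back definition, missing-value rule) and up to three columns in the data extract. No new patients or procedures are needed.

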### **Other Pre-specified Outcomes**

We will run the analysis described above on the following additional outcomes:

1. PCP appointment scheduled

PCP appointment scheduled (yes/no)

[Time Frame: within 60 days following day of discharge]

2. PCP visit

PCP appointment attended (yes/no)

[Time Frame: within 60 days following day of discharge]

3. Telehealth appointment scheduled

Telehealth appointment scheduled (yes/no)

[Time Frame: within 60 days following day of discharge]

4. Telehealth appointment attended

Telehealth appointment attended (yes/no)

[Time Frame: within 60 days following day of discharge]

5. Urgent care visit

Urgent care appointment attended (yes/no)

[Time Frame: within 60 days following day of discharge]

6. Call made to PCP

Record of patient call to PCP (yes/no)

[Time Frame: within 60 days following day of discharge]

7. Any of the suggested actions taken

PCP called or visited, urgent care visited, telehealth appointment attended, or PCP or telehealth appointment scheduled (yes/no)

[Time Frame: within 60 days following day of discharge]

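### Do the seven follow-through outcomes need their own significance level and multiplicity rule?

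*Combined protocol and SAP*

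**What the plan says.** The SAP's Planned Analyses section names one primary outcome, an ED visit within 120 days, and tags its analysis as confirmatory. The method is given as "We will run an OLS regression including a categorical predictor variable coding for experimental arm". No significance level appears there.

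The next section, Other Pre-specified Outcomes, continues: "We will run the analysis described above on the following additional outcomes". Seven binary outcomes follow, each over 60 days. Two concern primary care appointments (booked, kept), two concern telehealth (booked, kept), one is urgent care use, one is a call to the primary care office, and the seventh is the union of the other six. The section gives no level, ordering, adjustment or status for them.

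The one level in the document is in the Power Analysis: "with two-tailed alpha of .15, assuming a 41% baseline rate of subsequent ED visits within 120 days".

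On purpose, the Objectives section says "Data will be analyzed to determine which version is most effective at reducing ED use". The Background adds a second question, "whether patients followed through on the message-specific calls to action in the messages differently across conditions". Project Status records that "no data have been analyzed as of the time this document was uploaded".

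**The concern.** Follow-through is a question the study sets itself, yet the plan does not say what result would answer it. One analyst might carry .15 over from the power statement and another might use a conventional .05. They would then describe any outcome with a p-value between the two differently. With seven overlapping tests and no adjustment, a chance finding on one outcome could be presented as evidence that patients acted on the messages. At stake is how the follow-through results are described. The ED-visit conclusion is not involved.

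**Working it through.** **Inputs.** From the Power Analysis: 5,524 patients, 41% baseline, 3.0-point decrease, two-tailed .15, 80% power. From the SAP: seven further outcomes. Assumed: 1:1 allocation (2,762 per arm), and all event rates and correlations for the seven outcomes, none of which the document gives. The .05 level is a comparison value brought in from convention and is not in the document.

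**1. The plan's own figure.** With p̄ = .395,

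n per arm = [1.4395 × √(2 × .395 × .605) + 0.8416 × √(.41 × .59 + .38 × .62)]² / .03² = (0.9952 + 0.5816)² / .0009 ≈ 2,763,

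or 5,526 in total, against 5,524 stated. Power at 2,762 per arm is .7999. At two-tailed .05 the total would be 8,336, so .15 is the level on which the ED-visit comparison was sized.

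**2. Expected chance findings if outreach changes none of the seven.** This holds whatever the correlation: 7 × .15 = 1.05, of which 7 × .075 = 0.525 in the favourable direction. At .05 it is 7 × .05 = 0.35.

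**3. Chance of at least one.** With independent tests it is 1 − .85⁷ = .679 at .15 and 1 − .95⁷ = .302 at .05. Overlap lowers both. Simulated rates:

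| Assumption | at .15 | at .05 |
|---|---|---|
| Equal correlation .5 | .548 | .229 |
| Equal correlation .9 | .295 | .113 |
| Union outcome, 75–90% of primary care and 80% of telehealth bookings kept | .54–.59 | .22–.25 |
| Union outcome, 97% of bookings kept | .47–.51 | .19–.21 |

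The last two rows treat kept appointments as a subset of those booked. The plan does not say this: a visit kept within 60 days may have been booked before discharge.

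**4. How often the choice of level decides whether anything is significant.** A result that passes .05 also passes .15, so the chance that something passes .15 while nothing passes .05 is the difference of the two columns:
- independent: .679 − .302 = .377
- correlation .5: .548 − .229 = .319
- correlation .9: .295 − .113 = .182

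In the union-outcome scenarios it is about 28–33%. A larger figure, 40–49%, is the chance that at least one outcome has p between .05 and .15. That counts datasets in which another outcome already passes .05, so it overstates how often the overall answer would turn.

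**5. The same in percentage points.** At an assumed 20% event rate, SE = √(2 × .2 × .8 / 2,762) = .01076. The thresholds are 1.4395 × .01076 = 1.55 points and 1.960 × .01076 = 2.11 points. A difference between these is described differently at the two levels, but the estimate and its standard error do not change.

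**6. The price of formal adjustment.** An effect with 80% power at .15 has a standardised size of 1.4395 + 0.8416 = 2.281. At unadjusted .05 its power is Φ(2.281 − 1.960) = .63. At the first Holm step, .15/7 = .0214, it is Φ(2.281 − 2.300) = .49.

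**7. The sections side by side.** Planned Analyses has one outcome, called primary, with a directional hypothesis and the confirmatory tag. Other Pre-specified Outcomes has seven, under a separate heading, with no hypothesis and no tag. The Objectives tie the analysis to ED use. The Background says the study will assess ED use and also examine follow-through. Each section gives the seven a lower rank.

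**The case for a change.** The best case for a change runs as follows. Other Pre-specified is not a synonym for exploratory. The analysis being rerun is the very one labelled confirmatory. The .15 was used to size a single comparison, with numbers driven largely by practical limits on duration, and that reasoning does not extend to seven more tests. A sentence settling level and status would cost no patients, data or power, and nothing had been analysed at upload.

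Part of this stands. The level and the status of the seven are inferred, and a clarifying sentence would do no harm.

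The rest is weaker than it looks. The confirmatory test also takes its .15 from the Power Analysis, because Planned Analyses states no level either. A reader who accepts that for ED visits has an equally natural reading for an instruction to rerun the same analysis. The analyst who uses .05 is importing a level the document never mentions, so it goes too far to say the plan itself supports opposite answers. Nor does the plan say that a significant result on any of the seven will count as proof of follow-through. Because all seven outcomes and their windows are listed in advance, reporting only the favourable ones would be visible.

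**Conclusion.** No change to the plan follows. This is missing detail that analysts can fill sensibly: report all seven differences with intervals, as results secondary to ED visits, and state the level used. The primary test, its error rate and "80% power to detect a 3.0% absolute decrease in ED visits between active and control arms" are unaffected.

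The chance-finding rate is not small if .15 is applied without adjustment: 1.05 expected, and roughly 47–59% for at least one under the assumed event rates and overlap. The overall answer depends on choosing .15 or .05 in roughly 18–38% of null datasets across the assumed correlations. Except for the expected counts and the independence figures, these rest on event rates and correlations the document does not give. They would matter if the plan staked a claim on these tests, and it does not.

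Formal adjustment would guard against a claim the plan does not make, and could cut power from 80% to 49% at the first step. Adjusted p-values for information would alter no decision, and reasonable statisticians differ on whether to give them for outcomes of this rank.

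### Message content differs by Geisinger-PCP status, but the follow-through outcomes are compared only in all patients pooled, which can dilute a telehealth effect by an unreported factor

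*Combined protocol and SAP*

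**What the plan says.** The Background section gives a second aim besides ED use: to examine "whether patients followed through on the message-specific calls to action in the messages differently across conditions".

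Treatment-arm content has a shared part and a part that depends on PCP status.

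- **Shared.** Objectives describes the arm as one that "encourages patients in non-emergent situations to call their primary care provider's office first and, if unavailable, to try urgent care". Methods says of the arm: "Patients in this arm will receive suggestions for non-ED alternatives for same-day care".
- **With a Geisinger PCP.** Objectives: "Patients with a Geisinger PCP are also provided with the appropriate contact number for their PCP". These patients also get links to the urgent care site and to a page on same-day options.
- **Without a Geisinger PCP.** Objectives: "Patients without a Geisinger PCP are encouraged to consider Geisinger's virtual (telehealth) care, with a corresponding hyperlink". Methods agrees: "Those without a Geisinger PCP will also be provided with a hyperlink to Geisinger's virtual care option".

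The confirmatory model under Planned Analyses is an OLS regression in which study arm is the only predictor named. Under Other Pre-specified Outcomes the instruction is "We will run the analysis described above on the following additional outcomes", followed by seven yes/no outcomes at 60 days: PCP appointment scheduled (1), PCP visit (2), telehealth scheduled (3), telehealth attended (4), urgent care visit (5), call to PCP (6), and any of these actions (7). No stratum, interaction or covariate for PCP status is mentioned, and the number of patients with a Geisinger PCP is not given.

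**The concern.** PCP status decides which message a treated patient receives, yet the analysis ignores it. For telehealth, the only explicit prompt in the documents goes to patients without a Geisinger PCP, while the test includes everyone. A response confined to the prompted patients is averaged with a group that was not shown that prompt.

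What is at stake is interpretation. A null pooled telehealth result could mean that the link did nothing, or that few patients were sent it, and the planned analysis cannot tell these apart. If someone splits the data by PCP status after seeing the results, that split is post hoc.

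**Working it through.** **1. The plan's own figure.** Inputs from Power Analysis: 41% against 38%, two-tailed alpha .15, 80% power, 5,524 patients. The allocation ratio is not stated, so 1:1 is assumed. The normal-approximation formula for two proportions gives 2,763 per arm, 5,526 in total. With 2,762 per arm, power is 79.99%. The figure reproduces and is not in dispute. N = 5,524 is used below because Project Status raises recruitment to 6,186 only to replace the 662 excluded patients (6,186 − 662 = 5,524).

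**2. Dilution.** Let g be the share with a Geisinger PCP and d the effect of the virtual-care prompt in those sent it. If the effect in the others is zero, the pooled difference is (1 − g) × d.

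**3. Power for telehealth (outcomes 3 and 4).** Assumptions not in the documents: 10% use in controls, 13% in treated patients sent the link (d = 3 points), and g of 50%, 70% or 90%. With z = 1.4395 for two-sided .15, se0 the standard error under no difference and se1 under the alternative,

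power = Φ((d − z·se0)/se1) + Φ((−d − z·se0)/se1).

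Example at g = 70%:

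- Pooled: d = 0.009, 2,762 per arm, se0 = se1 = 0.00823. Then (0.009 − 0.01185)/0.00823 = −0.346, giving 0.365. The opposite tail adds 0.006, for a total of 0.370.
- Restricted: d = 0.03, 2,762 × 0.3 = 829 per arm, se0 = 0.01567, se1 = 0.01566. Then (0.03 − 0.02256)/0.01566 = 0.475, giving 0.683.

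| Share with Geisinger PCP | Pooled difference | Power, pooled | Power, patients sent the link |
|---|---|---|---|
| 50% | 1.5 points | 64% | 85% |
| 70% | 0.9 points | 37% | 68% |
| 90% | 0.3 points | 18% | 37% |

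**4. PCP outcomes, using calls (outcome 6) as the example.** Assume 30% against 33% in Geisinger-PCP patients and no recorded calls in the others. At g = 50%, 70% and 90% the pooled differences are 1.5, 2.1 and 2.7 points. Power is 54%, 67% and 78% pooled, against 60%, 72% and 80% restricted. The gain is small.

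**5. Sensitivity to the zero-effect assumption.** If the shared content or the same-day page also raises telehealth use in Geisinger-PCP patients by about 1.2 points (g = 50%), 1.0 point (70%) or 0.7 points (90%), pooled power equals restricted power. With a 3-point rise in everyone, pooled power is 98%. For PCP calls, if patients without a Geisinger PCP go from 10% to 11%, pooled power is 65%, 73% and 80%, which is no lower than restricted power.

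**The case against.** The strongest reply is that the trial compares two arms, so the conditions in the Background aim are the arms, and a pooled contrast on each named action answers that aim. This stands in part: the pooled contrast is a valid randomised estimate for the outreach as delivered, and no document states an aim of ranking the two message versions. It does not remove the problem that the aim concerns message-specific prompts while no planned estimate is tied to who was sent which prompt.

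The second reply is that much of the content is shared. Objectives describes the advice to call the PCP first and then try urgent care for the arm as a whole, and the PCP-dependent items are additions to it. This stands for outcomes 1, 2, 5 and 6: patients without a Geisinger PCP may have had the advice and lacked only the number and links. It carries less weight for telehealth, where the explicit prompt is described for one group only. The same-day page might list virtual care, but its content is not given.

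The third reply is that restricting to one stratum costs patients and helps only if the other stratum hardly responds. Step 5 of the working bears this out. It is a reason not to demote the pooled analysis; it is no reason to omit the stratum estimates.

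A reader might go further and infer that every follow-through outcome is answered mostly in patients not sent the relevant prompt. The documents do not support that. On the simple split, the share without the PCP items is 1 − g and the share without the virtual-care prompt is g. These sum to 1, so both cannot exceed one half, and g is not reported. A reader might also infer that outcome 7 credits actions the patient was never offered; as a composite over what the arm as a whole suggests, it is acceptable.

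**Conclusion.** The point holds as a matter of dilution and interpretation, chiefly for outcomes 3 and 4. If the telehealth effect is confined to patients without a Geisinger PCP, the pooled effect shrinks in proportion to their share: from 3.0 points to between 1.5 and 0.3 when 50% to 90% have a Geisinger PCP, with roughly 20 to 30 points of power lost. Those sizes rest on an assumed 10% control rate, an assumed 3-point effect, 1:1 allocation, and no effect in the other stratum. They are illustrations, because the documents give neither the PCP share nor any telehealth rate.

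For outcomes 1, 2 and 6 the mismatch is weaker, since only the phone number and links are specific to Geisinger-PCP patients. The benefit there is mainly an estimate that describes the patients given the number.

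It would be wrong to conclude that the pooled estimates are biased or that the confirmatory result is at risk. The arm comparison remains randomised, and the ED-visit test is untouched.

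**What to change.** Under Other Pre-specified Outcomes, keep the seven pooled analyses and add:

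- for outcomes 3 and 4, the arm comparison among patients without a Geisinger PCP at index discharge;
- for outcomes 1, 2 and 6, the arm comparison among patients with a Geisinger PCP at index discharge;
- one definition of PCP status, taken at index discharge and applied identically in both arms, so that each comparison stays randomised;
- the number of patients in each stratum, by arm.

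Outcome 7 can stay as it is.

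The cost is a few lines of SAP text and a filter on a variable that already selects message content. Project Status says no data had been analysed when the document was uploaded; if that is still so, the addition can be pre-specified. The downside is five more secondary tests, each on fewer patients, with no gain in power if the shared content also moves the other stratum. The pooled results stay in the report, so that possibility remains visible.
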